[iii] Study Population

Subjects will be drawn from the population of infants being treated at QECH.

[iv] Study Period

We anticipate the study will take 2-3 months.

[v] Sample Size

This study will enroll up to 60 infants at Queen Elizabeth Central Hospital. Up to 30 subjects will be collected from the neonatal ward and 30 subjects from the KMC ward. This sample size will ensure that we are able to collect sufficient data from infants with a range of gestational ages, weights, temperatures, and treatment locations (ie open cot, radiant warmer). The data from this study can be used to calculate the sample size needed in a larger study to evaluate changes in outcomes and nurse behavior related to the different temperature monitors.

Inclusion criteria:

1. The subject is currently being treated at QECH in the neonatal or KMC ward.
2. Study devices are available for use.
3. The subject's caregiver has provided informed consent for their child to participate.

The subject may be excluded from the study at the clinician's discretion for any reason including potential for skin irritation, cough or other condition that may preclude use of the temperature belt, or concurrent treatments that may require increased patient care.

If a patient is not enrolled in the study, the patient will receive the standard of care.

Informed Consent:

The investigator will provide details of the study to all eligible subjects' guardian and answer all questions. Fully informed and signed consents will be obtained from the subject's guardian prior to the start of any study procedures.

Documentation of the consent process will include the following elements:

- Date and time of consent;
- Topics discussed with the subject's guardian (e.g. risk, benefits, etc.); and
- Confirmation that the consent was reviewed, that the guardian's questions were answered, and that a signed copy of the consent was provided to the subject's guardian.

Potential Benefits and Compensation of the Proposed Research to Human Subjects and Others: Neonates and infants at risk for hypothermia may benefit from participating in this study as alternative forms of accurate and frequent monitoring may not be readily available. This study may benefit infants in the future as the accuracy and usability of the test devices can be used to improve access to temperature monitoring equipment in the future.

[vi] Data Collection

Training:

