The accuracy of the temperature sensors will be determined by calculating the difference between the temperatures recorded by the temperature sensor and the commercial patient monitor at each point in time. The average error between the temperature sensor and the gold standard will be calculated for each subject and compiled in a Bland-Altman plot. The 95% limits of agreement will be calculated. Our target error is less than +/- 0.5 C.

For the devices that do not provide a continuous numerical reading, the recorded state every hour will be compared to the gold standard at that point in time. The sensitivity and specificity for hypo/hyperthermia will be calculated for each device.

The ability of each device to accurately diagnose hypothermia will also be calculated with respect to the alarm events for each device for which they were recorded. The sensitivity and specificity will be determined using the number of false alarms collected during the study.

As a secondary analysis, the errors will be plotted against thermal treatment type and ambient temperature to determine their confounding effects on accuracy. An ANOVA will be used to determine statistical significance.

The research team from Rice University and QECH will be responsible for all data analysis. We plan to analyze data using Excel, MATLAB, and associated statistics packages.

[viii] Results Presentation

Statistical analysis will be performed and means, limits of agreement, sensitivities and specificities will be reported. Tables and graphs may also be used to present any additional correlations, explain outliers, or demonstrate confounding effects.

[ix] Dissemination of Results

The results of this study will be made available to the Ministry of Health, COMREC, the College of Medicine Library, the Department of Paediatrics, and other partners working in neonatal and child health. A copy of the final report and any published papers or abstracts will be submitted to The Health Sciences Research Committee and the University Research and Publication Committee (URPC) through the COMREC Secretariat. Findings will be published in academic journals and conference

proceedings in an effort to disseminate results to potential end-users. The research findings of this study will be critical in the evaluation of future interventions.

I. Ethical considerations

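### The only formal test of whether thermal treatment affects accuracy compares mean errors, so a non-significant result cannot support accuracy within ±0.5 °C in each treatment

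*Combined protocol and SAP*

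**What the plan says.** Section H [vii], Data Management and Analysis, defines accuracy by "calculating the difference between the temperatures recorded by the temperature sensor and the commercial patient monitor at each point in time". It then says "The average error between the temperature sensor and the gold standard will be calculated for each subject and compiled in a Bland-Altman plot", followed by "The 95% limits of agreement will be calculated" and "Our target error is less than +/- 0.5 C".

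The secondary analysis is described in two sentences. First, "the errors will be plotted against thermal treatment type and ambient temperature to determine their confounding effects on accuracy". Second, "An ANOVA will be used to determine statistical significance". The ANOVA's response, factors, unit of analysis and handling of repeated readings are not stated. No absolute or squared error is named, and neither limits of agreement nor a test of spread is planned by treatment.

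Section H [viii] adds an optional output: "Tables and graphs may also be used to present any additional correlations, explain outliers, or demonstrate confounding effects".

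Three design facts bear on the point:
- Section H [v]: "This study will enroll up to 60 infants at Queen Elizabeth Central Hospital", split as up to 30 from each of two wards, with no power calculation for this analysis.
- Section G names four care settings: open cots, hot cots, radiant warmers and the KMC ward.
- Section H [vi] has current thermal treatment and ambient temperature recorded hourly or at alarms, over up to 3 days. Treatment can therefore change within an infant.

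**The concern.** The question posed is about accuracy, and the plan's own yardstick for accuracy has two parts, bias and spread. The test named for that question addresses only the first. A device could read too high at some times and too low at others under one form of warming. Its mean error there would be near zero while its limits of agreement went well past ±0.5 °C.

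The sample size is justified partly by coverage of different treatment locations, so whether a device holds its target in each setting is something the study is meant to inform. If the ANOVA is not significant and nothing else is reported by treatment, the reader has no quantified evidence on that question.

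**Working it through.** **No plan figure to reproduce.** The documents give no SD, alpha, power or group size for this analysis. All SDs, group sizes, the 5% level and normal errors below are assumptions. From the documents come the ±0.5 °C target, the total of 60 infants, and up to 3 days of hourly readings (3 × 24 = 72 per infant).

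**1. Spread alone can fail the target.** With zero mean error, the limits are ±1.96 × SD and the share of errors within ±0.5 °C is 2Φ(0.5/SD) − 1.

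| SD (°C) | 95% limits (°C) | Share within ±0.5 °C |
|---|---|---|
| 0.15 | ±0.29 | 99.9% |
| 0.20 | ±0.39 | 98.8% |
| 0.40 | ±0.78 | 78.9% |
| 0.45 | ±0.88 | 73% |

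**2. What the ANOVA does in that case.** Simulation with one value per infant, all means zero and 60 infants:

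| SDs (°C) | Group sizes | ANOVA on errors rejects | Brown-Forsythe test of spread rejects |
|---|---|---|---|
| 0.15, 0.15, 0.45 | 20/20/20 | 7% | 99% |
| 0.15, 0.20, 0.40 | 20/20/20 | 7% | 92% |
| 0.20, 0.20, 0.20, 0.40 | 15/15/15/15 | 7% | 61% |

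In balanced groups the ANOVA stays close to its nominal 5% although one treatment clearly misses the target.

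**3. Unequal groups.** With SDs of 0.15, 0.15 and 0.45 °C, the ANOVA rejects in about 2% of studies at sizes 15/15/30, about 20% at 25/25/10 and 32% at 27/28/5. The means are equal throughout. The rate falls when the wide-error group is large and rises when it is small, because the pooled variance misstates the variance of the group means. Such a rejection is not detection of wider error.

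**4. Unit of analysis.** Suppose only within-infant error widens: between-infant SD 0.15 °C, within-infant SD 0.13 °C in the reference treatments and 0.37 °C in one treatment, 72 readings each.
- SD of a single error, reference: √(0.15² + 0.13²) = 0.198, limits ±0.39 °C.
- SD of a single error, wide treatment: √(0.15² + 0.37²) = 0.399, limits ±0.78 °C.
- SD of a per-infant average, wide treatment: √(0.15² + 0.37²/72) = 0.156, limits ±0.31 °C.

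Averaging within the infant removes the excess. On per-infant averages (3 × 20 infants) the ANOVA rejects in 5% of studies and Brown-Forsythe in 4%. A regular swing of ±0.4 °C within infants gives 5% and 4%, and an ANOVA on the absolute values of the averages gives 6%. If the absolute error is taken at each reading before averaging, rejection is essentially 100%.

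**5. Pooling readings and ignoring clustering.** In the same settings the ANOVA rejects in about 85% to 87% of studies. This is pseudo-replication. In the reference treatments the intraclass correlation is 0.0225/0.0394 = 0.57, so the design effect is 1 + 71 × 0.57 ≈ 41. An uncorrected F test is inflated on that scale even when treatments do not differ at all.

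**The case against.** **No rule equates non-significance with no effect.** A reader might infer that a treatment with wider error would be declared harmless. The documents do not support that. Section H [vii] has no such decision rule, and how a null result would be worded is a guess. This objection stands. The supportable claim is about what the test can show, not about what the investigators will say.

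**The errors are also plotted by treatment.** Wider spread could be visible. This stands in part: the spread would be untested rather than hidden, provided individual readings are plotted. If per-infant averages are plotted, within-infant swings disappear. In either case the plot has no limits or criterion by treatment.

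**The ANOVA will not always be non-significant.** A reader might infer that it misses wider error whatever the unit of analysis. It does not: unequal groups or pooled readings can make it reject. This stands, but those rejections come from group size or pseudo-replication and say nothing reliable about spread.

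**The response is unspecified.** That the ANOVA uses signed errors is an inference from the definition of error as a difference and from the Bland-Altman summary. It is the natural reading, since no other error is named. Likewise, nothing says that ambient temperature will be cut into groups; the plan is silent.

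**This is a secondary analysis in a self-described pilot.** True. The overall limits of agreement are not affected by this point, which limits its weight.

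**Conclusion.** The point holds as a mismatch between question and test. Accuracy is defined by bias and spread together, the only formal test of treatment effects compares means, and nothing by treatment is planned for spread. A non-significant ANOVA therefore cannot support accuracy within ±0.5 °C in each thermal treatment.

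The size is illustrative. Under the assumed SDs of 0.15, 0.15 and 0.45 °C with equal groups, the test rejects in about 7% of studies while one treatment has limits of ±0.88 °C and about 27% of errors outside the target (100% − 73%). With unequal groups the rate can be well below or well above 5%, for reasons unrelated to detecting spread. The direction of the conclusion does not depend on these values, but the percentages do.

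It is a cheap improvement to a secondary analysis and not a flaw in the main accuracy result.

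**What to change.** In section H [vii]:
1. State the response, factors and unit of the ANOVA, and keep it (or a mixed model with infant as a random effect) as the analysis of bias.
2. For each thermal treatment, report bias and 95% limits of agreement against ±0.5 °C, computed from individual readings, with intervals that allow for repeated readings per infant.
3. Add a reading-level analysis of spread by treatment, clustered by infant: either absolute error, with the absolute value taken before any averaging, or a model with treatment-specific variances. A test of spread on per-infant averages alone would not do, because it misses swings within an infant.
4. Enter ambient temperature as a continuous term.
5. State that any conclusion about treatment effects on accuracy will rest on both bias and spread.

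No new data are needed: for NTM, error is recorded automatically, and thermal treatment and ambient temperature are already to be recorded hourly. The cost is some extra analysis work. Intervals will be wide for treatments used in few infants, and should be reported as such.

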1. Prior to the start of the study, all study nurses/clinicians will receive training on how to use the test devices. Clinical decisions will still be based on the standard of care, which will not be interrupted during the study. The study nurse/clinician will apply the temperature sensors to the infant.
2. A research technician will be available for the duration of the study to record the data from the monitors.

Enrollment :

Enrollment will take place after fully informed and written consent from the parent or guardian. A parent will be free to withdraw their child from participating at any time, without explanation and without detriment to ongoing care. There will be no financial benefit to participants though the infants will benefit from close monitoring. A participant identification number will be assigned. This number will be used for identification purposes throughout the study.

Monitoring of Neonates:

During the trial, the following steps will be taken:

A trained study nurse will assess the subject for clinical complications before attaching the temperature monitoring device.

- 1) A trained study nurse or clinician will attach the three test temperature monitoring devices to the infant. A trained research assistant from Rice University or from the Biomedical Engineering Department at Malawi Polytechnic will observe all procedures and will notify the nurse of any observed errors so they may be corrected. They will also be able to answer any technical questions from the nurse.
- 2) The trained study nurse will attach the temperature probe from the commercial gold standard as well as provide any other care needed.
- 3) A research assistant will use a laptop to collect data from the continuous temperature monitors (NTM and gold standard). The nurse will record the temperature readings every hour from all monitors on paper forms along with the standard of care.
- 4) Each time an alarm sounds from any device (Bempu and the commercial gold standard have audible alarms), the nurse will record all temperature values including a reading taken with the standard of care method. If the subject is found to be hyper/hypothermic, the nurse will respond with the appropriate standard of care.
- 5) Temperature monitoring will continue for up to 3 days. The research assistant may ask the nurse to remove and reapply the temperature probes during this period.

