A research assistant will be available during the trial to mitigate any complications with the devices. If the subject's guardian, the nurse, or the research assistant indicates concern during the tests, temperature monitoring will be discontinued and the subject's treatment will return to the standard of care. The nurse can choose to remove one of the test devices and continue the study with the remaining monitors if any issue arises.

Clinical data will be collected on paper forms as is consistent with current clinical practice. Data from the temperature monitors will be saved on a secure study server for analysis. Clinical and/or research personnel will record information, excluding personal identifiers, on a standardized patient monitoring form. After the subject's participation is complete, a research assistant will collect and scan the form.

The following section details the variables that will be measured or calculated in the study.

Intended Data Collection:

1. Baseline demographic and relevant medical information
 - a. Recorded once at enrollment
 - i. Date of Study
 - ii. Date of Birth
 - iii. Sex
 - iv. Birth Weight
 - v. Type of delivery
 - vi. Gestational age at birth
 - vii. Corrected gestational age
 - viii. Abdominal circumference
 - ix. Admission Temperature
 - b. Recorded throughout study as clinically collected
 - i. Other comorbidities
 - ii. Medications/treatments given
 - iii. Current weight
 - iv. Additional temperature measurements taken as standard of care
2. Accuracy
 - a. Recorded automatically by study equipment
 - i. Abdominal temperature and alarms from Rice designed temperature monitor and gold standard device
 - b. Recorded every hour by study nurse or as alarm events occur
 - i. Temperature measurements from other devices
 - ii. Temperature measurements using standard of care method (axillary)
 - iii. Ambient temperature
 - iv. Current thermal treatment, if any
 - c. Movement/other caregiving
 - d. Fit/tightness of the devices

A log of observed user error and comments may be used to improve the usability of the test devices.

[vii] Data Management and Analysis

Personal identifiers will be removed from the data which will be kept on a secure server accessible only to study personnel.

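### The secondary analysis names only an ANOVA for significance: it does not say how ambient temperature enters the model and promises no estimate of its effect on device error

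*Combined protocol and SAP*

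**What the plan says.** Section H [vii] (Data Management and Analysis) describes the analysis in two sentences: "As a secondary analysis, the errors will be plotted against thermal treatment type and ambient temperature to determine their confounding effects on accuracy", followed by "An ANOVA will be used to determine statistical significance". Nothing further is said about the type of ANOVA, its terms, or the data unit it is applied to.

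Section H [vi], Intended Data Collection item 2b, lists "iii. Ambient temperature" under the line "Recorded every hour by study nurse or as alarm events occur". No bands or categories are attached to it. Current thermal treatment appears in the same list and is categorical by nature.

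The accuracy criterion, "Our target error is less than +/- 0.5 C", stands earlier in H [vii], with the Bland-Altman analysis. Section H [viii] (Results Presentation) promises sensitivities, specificities, means and agreement limits. It treats further correlations and displays of confounding as optional. No regression slope or confidence interval is promised anywhere.

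**The concern.** One unspecified method is to serve a categorical variable and a numeric one. Two problems follow.

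- **How ambient temperature is handled.** The ordinary use of an ANOVA is to compare groups. Used that way, ambient temperature must be cut into bands. The plan gives no cut points, so they could be chosen after the data are seen, and banding a numeric variable discards information.
- **What comes out.** The stated criterion is statistical significance. A p-value says whether an association is distinguishable from none. It does not say how many °C the error shifts between a cool ward and a warm one, nor how precisely that shift is known. The study covers open cots, hot cots, radiant warmers and KMC, so the size of the shift is what a user of the results would want.

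**Working it through.** The plan gives no figure to reproduce: there is no power statement, effect size or SD for this analysis. The checks below are illustrative, and their assumptions are marked.

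**Inputs from the documents.** Infants: up to 60 (H [v]: "This study will enroll up to 60 infants at Queen Elizabeth Central Hospital"). Duration: "Temperature monitoring will continue for up to 3 days" (H [vi]), so up to 3 × 24 = 72 hourly readings per infant. Target: ±0.5 °C (H [vii]).

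**1. Information kept if ambient temperature is grouped.** For a linear effect and k equal-sized groups, the share kept is the between-group variance divided by the total variance.

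- Normal distribution (assumed), k = 2: 2/π = 0.637.
- Normal, k = 3: group means −1.091, 0 and 1.091 SD; share = 2 × 1.091² / 3 = 0.793.
- Normal, k = 4: group means ±1.271 and ±0.325 SD; share = (1.271² + 0.325²) / 2 = 0.861.
- Uniform distribution (assumed): share = 1 − 1/k², giving 0.750, 0.889 and 0.938.

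**2. What that does to power.** Assumptions: one mean error per infant, N = 60, alpha 0.05, normal ambient temperature. The test is a noncentral F with noncentrality N × R²/(1 − R²). With grouping, R² is multiplied by the share kept and the numerator df are k − 1.

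| Assumed R² | Numeric term | 2 groups | 3 groups | 4 groups |
|---|---|---|---|---|
| 0.05 | 42% | 28% | 26% | 23% |
| 0.10 | 72% | 51% | 50% | 46% |
| 0.15 | 89% | 70% | 70% | 67% |

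More groups keep more information but spend more degrees of freedom, so power does not recover.

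**3. Is grouping unavoidable?** No. In one simulated data set of 60 infants, a linear model was fitted with treatment as a three-level factor and ambient temperature as a numeric covariate. The ANOVA table gave F = 5.996 on 1 and 56 df for ambient temperature, equal to the squared t statistic of its slope (5.996).

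**4. What the p-value leaves out.** That fit gave p = 0.017 and a slope of 0.029 °C of error per °C ambient, 95% CI 0.005 to 0.053. Over an assumed 10 °C ambient range, this is a shift of 0.029 × 10 = 0.29 °C, with a CI of about 0.05 to 0.53 °C. The interval runs from negligible to just beyond 0.5 °C, and the p-value alone shows none of this. Slopes that would by themselves produce a 0.5 °C shift are 0.5/5 = 0.10, 0.5/10 = 0.05 and 0.5/15 = 0.033 °C per °C for assumed ranges of 5, 10 and 15 °C.

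**5. Repeated readings.** H [vii] computes an average error per subject for the Bland-Altman plot but does not say whether the secondary analysis uses those averages or the hourly errors. With 72 readings per infant and an assumed intraclass correlation of 0.1 to 0.5, the design effect is 1 + 71 × 0.1 = 8.1 to 1 + 71 × 0.5 = 36.5. The 60 × 72 = 4,320 readings would then be worth about 533 to 118 independent ones. These figures apply in full to a covariate that varies mainly between infants. In that case an ordinary regression interval would be too narrow by a factor of √8.1 ≈ 2.8 to √36.5 ≈ 6.0.

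**The case against.** The strongest reply is that the plan has left a detail open, not chosen a wrong method. A reader might infer that naming an ANOVA forces ambient temperature into arbitrary groups. The documents do not support that: they never mention grouping, and step 3 shows that an ANOVA table can keep the variable numeric, from a fit that also yields a slope. The loss of information is therefore conditional on a reading the plan does not state. It is also smaller under a uniform distribution, and the two-group case is the worst one.

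The planned plot has error against ambient temperature, so a trend and any points beyond 0.5 °C would be visible, and correlations may be presented as well. It would be wrong to say that the analysis can reveal nothing about size. Nor do the documents give a check against ±0.5 °C as the reason for this analysis. They give confounding effects on accuracy as its aim and attach the target to the main accuracy analysis.

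All of that stands. A plot, however, carries no estimate or interval, and the correlations are optional. The only inference the plan commits to is a significance test. An ordinary regression would not be an adequate replacement either, because of the repeated readings within infants.

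**Conclusion.** The point holds in a limited form. The plan does not say how ambient temperature enters the ANOVA, and it commits to no effect estimate. That second gap remains however the ANOVA is read.

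If equal-sized groups are used and the effect is linear, the information lost is 36%, 21% or 14% for two, three or four groups under a normal distribution, and 25%, 11% or 6% under a uniform one. If ambient temperature is kept numeric, this loss does not arise. The distributions, R², intraclass correlation and ambient ranges used here are all assumptions; the documents give none of them.

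The importance is modest. This is a secondary analysis in a study described as a pilot. A reader might infer that the accuracy findings are undermined, but the Bland-Altman limits, sensitivity and specificity do not depend on it.

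**What to change.** Replace the ANOVA sentence in H [vii] with a linear mixed model of device error, or a regression with standard errors clustered by infant. Its terms should be:

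- ambient temperature as a continuous term, with a check for curvature;
- thermal treatment as a factor;
- an infant effect for repeated readings (in the clustered regression, the standard errors do this job).

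Report the slope in °C of error per °C ambient with a 95% CI. Also report the predicted mean error with its CI at the lowest and highest ambient temperatures observed, beside the ±0.5 °C target. State that a predicted mean does not describe the spread of individual errors. The model applies where a device gives a numeric reading; H [vii] already handles the others by recorded state. Keep the planned plot.

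The cost is a sentence or two in the plan, slightly more analysis work, and a linearity assumption to check. No extra data are needed, and MATLAB, already named in the plan, can fit the model.
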